## **16.2.4. Safety**

### **16.2.4.1. Analysis Population**

The safety population will be defined as all participants who received at least 1 dose of study treatment (i.e., the overall ITT population).

### **16.2.4.2. Methods of Analysis**

All AEs, laboratory data, ECG, neurological and physical examinations, and vital signs will be evaluated for safety.

#### **16.2.4.2.1. Adverse Events**

Only TEAEs will be presented in the summary tables. Treatment-emergent is defined as having an onset date that is on or after start of study treatment, or that is worsened after the start of study treatment.

Incidence of TEAEs will be summarized by treatment groups, overall, by severity, by relationship to LP, and by relationship to study treatment. SAEs, discontinuations and withdrawals due to AEs, AEs leading to hospitalization, and deaths will also be summarized or listed, depending on number of events. The summary tables will include incidence estimates for overall system organ class as well as for preferred terms within each system organ class. AEs will be coded using MedDRA. A subset of AE outputs will also be presented by disease progression subgroup (“participants who meet prognostic enrichment criteria for rapid disease progression”, “other eligible participants”).

#### **16.2.4.2.2. Clinical Laboratory Results**

Laboratory data will be summarized using shift tables. Shifts from baseline to high/low status for hematology and blood chemistry parameters, and shifts from baseline to high/positive status for urinalysis will be presented. In addition, the shift from baseline to the maximum postbaseline value and the shift from baseline to the minimum postbaseline status will be presented for each laboratory test by treatment group. Summary statistics for actual values and change from baseline will also be presented for quantitative laboratory data.

#### **16.2.4.2.3. Vital Signs**

The analysis of vital signs will focus on clinically relevant abnormalities.

#### **16.2.4.2.4. Electrocardiogram**

The number and percentage of participants with shifts to categorical values (abnormal not AE, or abnormal AE) will be summarized by treatment group.

#### **16.2.4.2.5. Columbia Suicide Severity Rating Scale**

The C-SSRS data will be summarized by treatment group.

CONFIDENTIAL

The information contained herein may not be used, disclosed, or published without the written consent of  
Biogen MA Inc.

## **16.2.5. Participant-Reported Outcomes on Quality of Life**

### **16.2.5.1. Analysis Population**

The analysis of the participant-reported outcome endpoints will be performed primarily for the mITT population but also for the non-mITT population.

### **16.2.5.2. Methods of Analysis**

The quality of life measures will be analyzed using an ANCOVA with MI with fixed effect for treatment and covariates for corresponding baseline value, baseline disease duration since symptom onset and use of riluzole or edaravone. The treatment difference at Day 197 will be derived from the model. Treatment differences at other visits will also be derived from the model for exploratory purpose. Nominal p-values will be presented.

### **16.2.6. Interim Analyses**

There will be no interim analysis performed.

### **16.2.7. Sample Size Considerations**

For Part C, approximately 99 participants will be randomized, with approximately 66 participants administered BIIB067 100 mg and approximately 33 participants administered placebo in a 2:1 ratio.

This sample size for Part C is selected primarily based on the JRT combining the Week 28 change from baseline in ALSFRS-R and mortality in the mITT population (N = 60). The observed results from an interim analysis of Study 233AS101 in participants who met the prognostic criteria for rapid disease progression as well as the observed ALSFRS-R slope decline in participants who received placebo in a similar ALS population with SOD1 mutation [Benatar 2018] are the basis of assumed treatment effect and the variability. Participants from both datasets were matched with the prognostic criteria for rapid disease progression specified in this protocol for Part C (i.e., one of the protocol-defined SOD1 mutations and a prerandomization ALSFRS-R slope decline of  $\geq 0.2$  per month or a prerandomization ALSFRS-R slope decline of  $\geq 0.9$  with SOD1 mutation NOT on the protocol-defined list). This resulted in a total of 12 placebo control participants who met the prognostic criteria for rapid disease progression (8 from the historical placebo data [Benatar 2018] and 4 from Study 233AS101) and 4 matched participants treated with BIIB067 100 mg from interim data of a very small cohort in Study 233AS101. The observed mean slope of decline was -3.83 for the matched placebo participants and -0.74 for the matched BIIB067 100 mg participants, with a pooled SD of 3.166. In the 12 matched participants on placebo, there was 1 death and 2 participants with permanent assisted ventilation less than 6 months but none in the BIIB067 100 mg matched participants. Based on this and overall survival data in patients who met the prognostic criteria for rapid disease progression from the literature on patients with an A4V SOD1 mutation, the survival at Week 28 was assumed to be 82% in the placebo control and 90% in the BIIB067 100 mg group.

Under the above assumptions, with N = 60 participants in the mITT population and a two-sided significance level of 0.05, the JRT gives 84% power. Because events of death have been factored into the analysis, no sample size overage is planned for missing values.

CONFIDENTIAL

The information contained herein may not be used, disclosed, or published without the written consent of Biogen MA Inc.

For the non-mITT population, the primary focus will be on the PD endpoint, CSF total SOD1 protein concentration, as this population is anticipated to have a slower decline in clinical function compared to the mITT population. A sample size of 26 participants in the treated group and 13 participants in the placebo group for the non-mITT population would provide 97% power to detect a 25% reduction in CSF total SOD1 protein from baseline in the treated group, with an assumed SD of 0.216 (natural log scale), compared to the placebo group.

CONFIDENTIAL

The information contained herein may not be used, disclosed, or published without the written consent of Biogen MA Inc.

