## **10. DISCONTINUATION OF STUDY TREATMENT OR WITHDRAWAL OF PARTICIPANTS FROM THE STUDY**

### **10.1. Withdrawal from the Study (Part A) or Discontinuation of Study Treatment (Parts B and C)**

A participant *must* be withdrawn from Part A of the study (SAD), or permanently discontinue study treatment in Part B (MAD) and Part C (Pivotal) of the study, for any of the following reasons:

- The participant becomes pregnant. Study treatment must be discontinued immediately. Report the pregnancy according to the instructions in Section [15.4.1](#).
- The participant withdraws consent to continue study treatment.
- The participant experiences a medical emergency that necessitates permanent discontinuation of study treatment.
- The participant experiences a medical emergency that necessitates unblinding of the participant's treatment assignment.
- The participant is unwilling or unable to comply with the protocol.
- At the discretion of the Investigator or Sponsor.

The reason for discontinuation of study treatment must be recorded in the participant's CRF.

Participants who discontinue treatment in Part B may remain in the study and continue protocol-required tests and assessments.

Participants who discontinue study treatment in Part C will be encouraged to remain in the study and complete all appropriate protocol-specified tests and assessments. It is recommended that participants who terminate early (i.e., discontinue both study treatment and study assessments) perform the assessments of the EOS Visit (Week 28 Visit) within 4 weeks after the last dose of study treatment. Home assessments will be allowed at the discretion of the Investigator for participants who cannot come to the site in person for their Early Termination Visit.

CONFIDENTIAL

The information contained herein may not be used, disclosed, or published without the written consent of Biogen MA Inc.

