#### **16.2.1.2. Methods of Analysis**

##### **16.2.1.2.1. Analysis of the Primary Efficacy Endpoint**

The primary efficacy endpoint is the change from baseline to Week 28 in the ALSFRS-R total score, which will be analyzed as follows, depending on 2 scenarios:

CONFIDENTIAL

The information contained herein may not be used, disclosed, or published without the written consent of  
Biogen MA Inc.

1. If the number of deaths across both treatment arms is  $\geq 3$  (i.e.,  $\geq 5\%$  deaths out of a total of 60 patients in the mITT population), the JRT methodology to account for mortality [Berry 2013] will be used for the primary inference. When implementing the JRT methodology, MI will be used to handle withdrawals. The estimates will be obtained from an ANCOVA for change from baseline in ALSFRS-R at Week 28 with missing data imputed using MI. The corresponding nominal p-value from the ANCOVA will be presented as a sensitivity analysis.
2. If the number of deaths is  $< 3$  (i.e.,  $< 5\%$  deaths out of a total of 60 patients in the mITT population), ANCOVA with MI will be used as the primary analysis method for both inference and estimates. The p-value from the JRT will be presented as a sensitivity analysis.

The primary estimand is described as follows:

The primary analysis for the primary endpoint is the composite estimand [ICH 2017]. The estimand of the primary analysis is defined as follows:

- Population: all participants in the mITT population.
- Variable: change from baseline to Day 197 in the ALSFRS-R total score.
- Handling of intercurrent events: Relevant intercurrent events are handled using a composite strategy in which participants who have these intercurrent events are ranked against each other and against participants without any intercurrent event using the joint rank methodology based on MI datasets. The relevant intercurrent events are deaths and withdrawals. These participants will be handled using the composite strategy and ranked as described in this section. For withdrawals, this will be based on the imputed value for Day 197 from the MI datasets.

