- Summary statistics: difference between treatment groups in least square means of Day 197 change from baseline with corresponding standard errors and 95% confidence intervals taken from the ANCOVA for change from baseline to Day 197, based on the MI datasets. The ANCOVA model will include treatment group as a fixed effect and covariates for ALSFRS-R total score, baseline disease duration since symptom onset, and use of riluzole or edaravone.

For the JRT analysis, the ranked scores will be analyzed for each of the 100 MI-complete datasets using an ANCOVA model with treatment included as a fixed effect and adjusted for the following covariates: baseline disease duration since symptom onset, baseline ALSFRS-R total score, and use of riluzole or edaravone. The p-value will be based on combining the estimates for the treatment differences using PROC MIANALYZE. The difference between treatment groups in median changes from baseline to each visit will be presented with 95% confidence intervals based on the MI datasets, as well as the p-value from the JRT for Day 197. The joint rank analysis will only be performed for the mITT population.

The joint rank procedure allows for a statistical test of the treatment effect on the ALSFRS-R total score while accounting for truncation of data due to deaths. In this analysis, a participant's joint rank score will be calculated by comparing each participant to every other participant in the

CONFIDENTIAL

The information contained herein may not be used, disclosed, or published without the written consent of  
Biogen MA Inc.

study, resulting in a score of +1 if the outcome was better than the participant being compared, -1 if worse, and 0 if the same. The participant's score will then be calculated by summing their comparison to all the other participants in the study.

For the purpose of this calculation, participants will be grouped into the following 2 categories:

- Group 1: Participants who complete the study and have data available at the Day 197 assessment AND participants who withdraw from the study due to reasons other than death
- Group 2: Participants who die

MI will be used to impute all missing data before determining the rank score, including intermittent data and data after withdrawal from the study except after death.

In each of the 100 imputed datasets, participants will be ranked as follows:

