- Participants in Group 2 will be given lower ranks than participants in Group 1, with the lowest ranks being given to the participants who die in the shortest time after first dose. Progressively higher ranks will be given to participants who die at longer times after first dose.
- Participants in Group 1 will rank higher than participants in Group 2. Progressively higher ranks will be given to participants with a higher change from baseline at Day 197, i.e., a smaller decline at Day 197.

Further details will be described in the statistical analysis plan.

The primary inference will be based on the mITT population. The treatment comparison will be based on a 2-sided  $\alpha$  level of 0.05.

If the second scenario occurs, i.e., in both the active and placebo treatment groups combined the number of participants who died is  $< 3$  (e.g.,  $< 5\%$  deaths out of a total of 60 participants in the mITT population), the primary efficacy analysis will be the change from baseline in ALSFRS-R total score, analyzed using an ANCOVA based on data imputed using MI. The ANCOVA model will include treatment group as a fixed effect and covariates for each of the corresponding baseline value for ALSFRS-R total score, baseline disease duration since symptom onset and use of riluzole or edaravone. The primary inference will be based on the treatment comparison at Week 28. A 2-sided  $\alpha$  level of 0.05 will be used. Treatment differences at other visits will also be presented with nominal p-values.

Sensitivity, supplementary and subgroup analyses of the primary efficacy endpoint will be specified in the statistical analysis plan.

For the non-mITT population, the analysis will be the change from baseline in ALSFRS-R total score, analyzed using an ANCOVA based on data imputed using MI. The ANCOVA model will include treatment group as a fixed effect and covariates for each of the corresponding baseline value for ALSFRS-R total score, baseline disease duration since symptom onset, and use of riluzole or edaravone. Least square means with standard errors will be presented for each treatment group. The difference between treatment groups in least square means for change from baseline at each visit, with corresponding standard errors and 95% confidence intervals, will be presented with nominal p-values.

CONFIDENTIAL

The information contained herein may not be used, disclosed, or published without the written consent of  
Biogen MA Inc.

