**analysis for each endpoint will also be repeated for the non-mITT population with nominal p-values presented.**

**Rationale:**

The hierarchy for the sequential closed testing procedure has been modified to account for the likelihood of statistical success for each endpoint in the 28-week duration of this study. CSF SOD1 and plasma NfL are also now included in the closed testing procedure and placed above SVC. Due to the COVID-19 pandemic, the level of missing data for SVC is likely to be higher due to individual site restrictions for handling the pandemic. The time-to-event endpoints are ranked lowest as the duration of the study and the inclusion criteria for  $SVC \geq 65\%$  at Screening in the mITT population reduces the chance to observe a large number of events in these endpoints over 28 weeks. It is expected that a greater treatment effect may be observed on SVC and muscle strength measured by HHD than on the time-to-event endpoints.

Change from baseline in SVC will be analyzed similarly to change from baseline in ALSFRS-R to account for mortality, depending on the number of deaths. The analysis specified provides a more robust method for estimating the treatment effect on this endpoint.

ANCOVA with multiple imputation is also specified as the analysis of HHD megascore instead of MMRM to provide a more robust method for handling missing data.

Section 6.2.1.2 Secondary Efficacy Endpoints

**Change:** The time to event endpoints were renamed so that VAFS was relabeled as time to death or permanent ventilation; and overall survival was renamed to time to death.

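### Does citing deaths as the reason for no missing-value overage leave withdrawals out of the Part C sample size?

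*Protocol*

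**What the plan says.** Section 16.2.7 assumes Week 28 survival of 82% on placebo and 90% on BIIB067, and ALSFRS-R means of -3.83 and -0.74 with pooled SD 3.166. It reports that with N = 60 and "a two-sided significance level of 0.05, the JRT gives 84% power". The mITT paragraph then ends: "Because events of death have been factored into the analysis, no sample size overage is planned for missing values". A separate paragraph on the non-mITT population follows.

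Section 16.2.1.2.1 describes the test being powered. Those who die form Group 2: "Participants in Group 2 will be given lower ranks than participants in Group 1". Group 1 holds completers together with "participants who withdraw from the study due to reasons other than death". MI is used to "impute all missing data before determining the rank score, including intermittent data and data after withdrawal from the study except after death", and for scenario 1 the section adds: "When implementing the JRT methodology, MI will be used to handle withdrawals".

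Section 10.1 bears on how much will be missing: "Participants who discontinue study treatment in Part C will be encouraged to remain in the study".

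**The concern.** The sentence draws a conclusion about missing values from a fact about deaths. In the JRT a participant who dies has an observed outcome, a rank at the bottom ordered by time of death. The values that are missing belong to participants who withdraw alive or skip a visit. Factoring in deaths does nothing for them, and Section 16.2.7 states no withdrawal rate, not even zero.

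MI keeps withdrawn participants in the ranking but cannot restore information that was never collected. If withdrawals were common, the pivotal comparison could have less than its quoted 84% power, and a reader of Section 16.2.7 could not tell at what rate that would happen.

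**Working it through.** **Inputs from the protocol.** N = 60 at 2:1 (Section 9.2), so 40 active and 20 placebo. Difference in means 3.83 - 0.74 = 3.09; SD 3.166; survival 0.90 and 0.82; two-sided alpha 0.05 (all Section 16.2.7).

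**Step 1: are deaths really in the 84%?** Ignoring deaths, a normal-approximation comparison of means gives
z = (3.09/3.166) / sqrt(1/40 + 1/20) - 1.96 = 0.976/0.2739 - 1.96 = 1.60, power 94.6%.
The stated 84% is far lower, so the premise of the sentence is true. Expected deaths are 40 x 0.10 + 20 x 0.18 = 7.6, leaving 52.4 survivors.

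**Step 2: reproduce the 84% with deaths ranked and no withdrawals.** By hand, the probability that an active participant outranks a placebo participant has three parts:
- both survive: 0.90 x 0.82 x Phi(3.09/(3.166 x sqrt 2)) = 0.738 x 0.755 = 0.557
- only the active participant survives: 0.90 x 0.18 = 0.162
- both die, active later: about half of 0.10 x 0.18 = 0.009

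The sum is 0.728. Noether's formula for a rank test gives sqrt(12 x 60 x (2/3)(1/3)) x 0.228 - 1.96 = 2.89 - 1.96 = 0.93, power 82%. That formula uses the null variance and is somewhat conservative here. Simulating the ranks directly (60,000 trials, exponential death times, pooled t-test on ranks) gives 85.9%. The stated 84% lies between the two.

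**Step 3: what could withdrawals cost?** The protocol gives no rate, so 5% to 20% is an assumption.

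| Withdrawal | MI from earlier visits | That share of each arm lost outright |
|---|---|---|
| 0% | 85.3 to 86.5% | 85.9% |
| 5% | 84.4 to 85.8% | 83.7% |
| 10% | 83.3 to 84.9% | 81.8% |
| 15% | 81.6 to 84.0% | 79.9% |
| 20% | 79.6 to 82.9% | 76.7% |

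The MI column (10,000 trials per setting, 30 imputations, covariate-adjusted ranks) assumes that survivors withdraw completely at random, a baseline covariate correlation of 0 or 0.3, and 70% or 90% of Week 28 variance due to individual slopes. The last column shrinks the arms to 38/19, 36/18, 34/17 and 32/16. It is pessimistic, because it discards visits that MI would use.

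A harsher case gives withdrawn participants in both arms placebo-like outcomes. Power is then about 83, 78, 74 and 70% at 5, 10, 15 and 20%. Most of that fall comes from diluting the treatment difference rather than from losing data.

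**Step 4: what the design does to limit loss of ALSFRS-R.** Section 10.1 keeps participants who stop treatment in follow-up and recommends the end-of-study assessments for early terminators. Table 3 and Section 13.1 allow home visits. Section 19.1 allows ALSFRS-R by telephone in a public health emergency. Only participants who leave assessment altogether, or miss Week 28, need imputing there.

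**The case for a change.** The best case for a change is that the protocol itself offers a reason, so this is not detail left to the SAP. That reason fails on the protocol's own terms, and one sentence would mend it. The stated inputs also reproduce the power with nobody withdrawing, which suggests that no allowance was made.

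The first part stands: the reason is incomplete. The second is weaker. The reproductions run from 82% to 86% depending on the test and variance used. That spread is wide enough to hide a small allowance for withdrawal, so the document cannot show whether one was made. For the same reason, any withdrawal rate at which a reviewer's simulation crosses 84% reflects the small gap between two models and is not a usable cut-off.

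Support has also been sought in the rationale for the current version, which expects that "the level of missing data for SVC is likely to be higher due to individual site restrictions". That passage concerns slow vital capacity, a secondary endpoint, and says nothing about ALSFRS-R.

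Finally, a fuller sentence would need the sponsor's own assumed withdrawal rate. Writing it in, even as zero, would leave 60 participants, the same test and the same imputation.

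**Conclusion.** No change is called for. The sentence is loosely argued: it explains why deaths need no overage and is silent on withdrawals. Read in context, its sense is clear enough. The large, disease-driven loss of Week 28 scores is already in the power, and Section 16.2.1.2.1 says how the remaining gaps are handled.

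The 84% reproduces on the stated inputs (82% by formula, about 86% by simulation). At an assumed 10% withdrawal of survivors the loss under MI is about 2 points; at 20% it is roughly 4 to 6. A full overage at 10% would be 60/0.90, or 67 participants, and that overstates the need because MI uses the earlier visits. In a mutation-defined form of a rare disease, accepting a couple of points of power in place of seven more rapidly progressing participants is a fair trade-off.

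This rests on modest withdrawal and on withdrawn participants resembling those who stay. Placebo-like outcomes after withdrawal would cost more, about 8 points at 10%, but that is a question of effect size that rewording this sentence would not address.

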## **17. ETHICAL REQUIREMENTS**

Biogen and the Investigator must comply with all instructions, regulations, and agreements in this protocol and applicable ICH and GCP guidelines and conduct the study according to local regulations.

The Investigator may delegate responsibilities for study-related tasks where appropriate to individuals sufficiently qualified by education, training, and experience, in accordance with applicable ICH and GCP guidelines. The Investigator should maintain a list of the appropriately qualified persons to whom significant study-related duties have been delegated.

